4.1 Screening/Enrolment period

At screening, subjects are assessed to ensure that they meet eligibility criteria. Once the subject signs the ICF, they are considered enrolled in the study. Subjects who do not meet these criteria must not be randomised into the study. These subjects will be considered as screen failures (See Section 3.10).

Screening procedures will be performed according to the Screening Study Plan (Table 2), from Day 30 to Day -1. Screening visit may be conducted as multiple visits, S1, S2, Sx, where laboratory evaluations can be completed initially.

Chest X-rays, renal biopsy, and Pap smears may be completed any time during the screening period as long as all results have been reviewed by the Investigator prior to randomisation.

If a subject does not meet eligibility criteria on the basis of a laboratory value then the laboratory parameter may be repeated once within the screening period.

On rare occasion an extension of the 30 day screening window may be allowed if the re-collection of the 24-hour UPCR or other required samples is necessary or if the results needed for randomisation are delayed. Before the Week 0 (Day 1) visit, a notification from the study Sponsor/Designee Medical Monitor should be obtained, confirming that subject meets LN diagnosis related eligibility criteria. The details of eligibility confirmation process will be documented separately for the site (Site Manual), and for the study team (Eligibility Process).

4.1.1 Re-screening subjects who screen fail

If a subject fails screening for reason(s) which, in the opinion of the Investigator, may change to make the subject eligible, the subject may be re-screened one time. In this case, the subject will re-sign the informed consent document and all screening procedures will be performed except those assessments which may be still within the specified periods (eg, chest X-ray, renal biopsy, TB test). If a subject does not meet eligibility criteria on the basis of a laboratory value, then the laboratory parameter may be repeated once within the screening period; this will be re-testing so that re-screening is not required. If the subject fails screening twice, they may not undergo further screening for this study except on a case by case basis, after discussion and approval from the Sponsor/Designee Medical Monitor.

4.1.2 Medical history

A complete medical history by body system will be completed during screening. This will also include history of allergies and anaphylaxis, concomitant diseases, viral reactivation events, and previous manifestations of SLE. Various risk factors for atherosclerosis will be assessed as part of the demographics at screening. On Day 1, the medical history will be reviewed and any changes since screening will be documented, if applicable.

4.1.3 SLE and LN medication history

All prescription medications the subject has ever taken for SLE and LN should be documented in the subject's file (except for only minor dose adjustments if these were done >3 months prior to the ICF signature date), including prior use of cyclophosphamide, MMF, oral and parenteral corticosteroids; if these were discontinued, then reasons for discontinuation must be included. Any medications ongoing at the time of informed consent or received following signing the ICF are considered concomitant medications. Any non-prescription medications, eg, naturopathic or ayurvedic remedies ever used for SLE or for any other purpose should be documented, as well as continuing use of any non-prescription remedies not excluded from use during the study period.

4.2 Treatment period

Procedures during the treatment period will be performed according to the Treatment Period Study Plan ([Table 2](#) and [Table 4](#)), from Week 0 (Day 1) to Week 104. The patient-reported outcome assessments should be completed by the subject prior to all other evaluations, and prior to the infusion, as disease assessments/clinical evaluations may confound the results.

On Day 1, in addition to the eligibility confirmation by study Medical Monitor/Designee, the Principal Investigator must ensure that the subject still meets eligibility criteria, including Day 1 assessments according to the Treatment Period Study Plan ([Table 2](#)).

Subjects confirmed to be eligible will be randomised.

Subjects will have scheduled visits at 4-week intervals to complete protocol-specified assessments and IP administration according to the Treatment Period Study Plan ([Table 2](#)).

The primary endpoint will be assessed at Week 52. For subjects who prematurely discontinue IP and are not willing to continue to participate in the study refer to [Section 3.9](#).

The SLE Data Medical Review Team ([Section 9.2.4](#)) will perform an ongoing review of all SLE and LN data in conjunction with the relevant AE, concomitant medications and central laboratory data.

For subjects who meet withdrawal criteria for worsening LN at Week 24 or later and for subjects not achieving CRR at Week 52, a second renal biopsy may be performed at the discretion of the Principal Investigator based on clinical indication and local practice. A separate consent is required for this second biopsy.

4.2.1 Week 52 visit

Study objectives will be assessed at Visit 14 (Week 52). A 24-hour UPCr must be performed to assess the primary endpoint. Investigational sites should contact subjects prior to this visit in order to ensure the subject is compliant with the protocol to support the study objectives. Laboratory samples, including the 24-hour UPCr may be collected within 14 days prior to the

scheduled Visit 14(Week 50 - Week 52- see [Table 2](#) footnote b), so that results are available for determining if subjects are eligible for continued IP dosing in the second year of the study.

4.2.1.1 Assessment criteria for participation in the second year extension period (Week 52)

The 24-hour UPCR sample collected between Week 50 to Week 52 for the Week 52 response assessment will be used to assess criteria for participation in the second year extension period. The eGFR measured between Week 50 and Week 52 will be used to assess eligibility for participation in the second year extension period.

4.2.1.2 Initiation of dosing in the second year extension period (Week 52 to Week 60)

All efficacy and safety assessments for Week 52 must be completed prior to initiation of dosing in the second year extension period. The first dose in the second year extension period must be administered between Week 52 (+14 days) and Week 60. Prior to administering the first dose in the second year extension period, the Principal Investigator must confirm that all Week 52 safety assessments (including the ECG) are performed and that subject does not meet any withdrawal criteria. The Week 52 QFT-G test results must be available prior to Week 56 and results of the Pap smear must be found to meet eligibility requirements as described in [Appendix K](#) and available by Week 60 or IP administration will be discontinued.

4.2.1.3 Week 104 visit

The last dose of IP will be administered at Week 100. At Week 104, a 24-hour UPCR sample must be collected. Investigational sites should contact subjects prior to this visit in order to ensure the subject is compliant with the study procedure to support the study objectives. For subjects who discontinue IP between Week 52 and Week 100, and are not willing to continue to participate in the study refer to [Section 3.11](#).

4.2.2 Follow-up visits after premature discontinuation of investigational product

Subjects who agree to continue scheduled visits until Week 52 (if IP discontinued prior to Week 52) or Week 104 (if IP discontinued after Week 52):

Subjects who prematurely discontinue IP (see [Section 3.9](#)) should have a 24-hour UPCR measurement within 4 weeks of the decision to discontinue IP and before the start of a new treatment for LN.

Subjects who discontinue IP will be asked to return for all regular clinic visits. All study assessments will be performed if possible; however, at a minimum, the following assessments should be completed:

- Lupus Serology tests (anti-dsDNA antibodies, C3, C4)
- PGA (Physician's Global Assessment)

- 24-hour urine for protein, creatinine and spot UPCR

The following safety assessments should also be completed:

- Serum chemistry, haematology, urinalysis
- Vital signs
- Physical examination, weight
- Adverse events including AESIs
- TB Questionnaire
- Concomitant medications

Subjects who are unwilling to continue to Week 52 or Week 104:

If during the 52 week double-blind treatment period, the subject is unwilling to continue through Week 52, he/she should complete Week 52 visit and be followed for 12 weeks after the last administration of IP by completing the Follow-up Visits, unless consent is withdrawn. If during the second year extension period, the subject is unwilling to continue through Week 104, he/she should complete Week 104 visit and be followed for 12 weeks after the last administration of IP by completing the Follow-up Visits, unless consent is withdrawn.

If the subject does not agree to return for any clinic visits and perform the laboratory testing requirements of these visits, he/she will be asked if he/she can be followed on a monthly basis via telephone calls for 12 weeks after last dose of IP administration. At these calls, he/she will be asked about AEs/SAEs, lupus symptoms, and lupus medications. Steroid bursts will also be captured.

Subjects who withdraw consent:

If the subject indicates his/her intention to withdraw consent, attempts should be made to complete the Week 52/discontinuation or Week 104/discontinuation visit as applicable before the consent is withdrawn. However, no study procedures or data collection can occur after the subject withdraws consent.

Adverse events will be followed up per Section [6.5.2](#).

4.3 **Unscheduled visit**

There may be times a subject needs to have an unscheduled visit. Potential assessments for such a visit are listed on the Treatment Period Study Plan ([Table 2](#) and [Table 4](#)). The Investigator should determine and note the reason for the unscheduled visit and the

assessments to be completed based on the reason for the unscheduled visit. Concomitant medications and AEs should be completed whenever a subject has an unscheduled visit.

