3.9.9 Procedures for discontinuation of a subject from investigational product

Discontinuation of IP does not necessarily mean discontinuation of follow-up or termination of study participation. Subjects who are discontinued from the IP should be followed up to continue to undergo all study-related visits/procedures for the full treatment period (Table 2) in order to support the final efficacy and safety analysis for anifrolumab (see Section 8). Subjects who discontinue IP earlier than 12 weeks before Week 52 will be followed until Week 52. Those discontinued within 12 weeks prior to Week 52 will need to have follow-up beyond Week 52 to complete a 12 week safety observation period after the last dose of IP administration.

Subjects who discontinue IP in the second year extension period will be followed until Week 104. Those discontinued within 12 weeks prior to Week 104 will need to have follow-up beyond Week 104 to complete a 12-week safety observation period after the last dose of IP administration.

The reason for premature discontinuation of IP will be documented in the source documents and recorded in the eCRF.

It is essential to collect as much data as possible for all subjects throughout the study and especially all potential endpoint events. Complete withdrawal from the study (ie, withdrawal of consent) has a direct negative impact on the potential validity of all study data and should be avoided wherever possible. If the subject permanently discontinues IP prior to their completion of the study and wishes to continue with only selected study assessments; prioritised assessments are listed in Section 4.2.2.

For subjects who wish to withdraw from the study completely refer to Section 3.9.4.

If a subject is withdrawn from study, see Section 3.10.

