Visit Number	SV	1	2	3	4	5	6	7	8	9	10	11	12	13	14		UN ^a
Study Week	-	W0	W4	W8	W12	W16	W20	W24	W28	W32	W36	W40	W44	W48	W52/DC ^{b,1}		-
Visit Window	-		±7 D	±7D	±7D	±7D	±7D	±7D	±7D	±7D	±7D	±7D	±7D	±7D	±7D		
Steroid tapering		X	X	X	X	X	X	X	X	X	X	X					
Extra-renal flare (SLEDAI-2K based Flare Assessment Instrument)		X	X	X	X	X	X	X	X	X	X	X	X	X	X		X
Verify eligibility criteria	X	X															
Randomisation		X															
Ophthalmologic examination for chloroquine/hydroxychloroquine toxicity (if applicable) ^v	X	X															
IP administration		X	X	X	X	X	X	X	X	X	X	X	X	X	X ²		
Sponsor-provided MMF ^w		X	X	X	X	X	X	X	X	X	X	X	X	X	X		

ACR=American College of Rheumatology; ADA=anti-drug antibodies; AE=adverse event; AESI=adverse event of special interest; Anti-dsDNA=anti-double stranded deoxyribonucleic acid; C3=third component of complement; C4=fourth component of complement; C-SSRS=Columbia-Suicide Severity Rating Scale; DC=early discontinuation; dsDNA=double stranded deoxyribonucleic acid; ECG=electrocardiogram; eGFR=estimated glomerular filtration rate; FSH=follicle-stimulating hormone; IFN=interferon; IP=investigational product; PGA=Physician's Global Assessment; QFT-G=QuantiFERON-TB Gold; MDRD=Modification of Diet in Renal Disease formula; MMF=mycophenolate mofetil; MPA=mycophenolic acid; LN=lupus nephritis; PD=pharmacodynamics; PtGA=patient global assessment; PHQ-8=Personal Health Questionnaire Depression. Scale; PK=pharmacokinetic; PRR=partial renal response; RNA=ribonucleic acid; Sc=screening; SAE=serious adverse event; SLE=systemic lupus erythematosus; SLEDAI-2K=Systemic Lupus Erythematosus Disease Activity Index 2000; SLICC/ACR=Systemic Lupus International Collaborating Clinics/American College of Rheumatology; SV=screening visit; TB=tuberculosis; UN=unscheduled; UPCR=urine protein/creatinine ratio

a Not all assessments indicated for the Unscheduled Visit need to be performed. The assessments are to be performed at the discretion of the Investigator, as clinically indicated.

b Subjects with early discontinuation of IP should continue to attend visits according to the Study Plan. However a 24-hour UPCR sample should be collected within 4 weeks of IP discontinuation decision (unless the next scheduled visit is within 4 weeks of this decision, and includes this test already) and before the start of a new treatment for LN. If at any point after IP discontinuation is performed, the subject decides to discontinue from the study

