4.2.6.4 SLEDAI-2K-based flare assessment instrument

The flare rate per of subject years for extra-renal flares will be presented overall, and by timing ("on-treatment" and "off-treatment"), for mild/moderate flares, severe flares and any flares, respectively. An "on-treatment" flare is defined as a flare with a date of onset after the date of first dose of IP and on or prior to the date of last dose of IP + 28 days. An "off-treatment" flare is defined as a flare with a date of onset after the date of last dose of IP + 28 days. Where a flare has been marked as both mild/moderate and severe, it will be considered to be severe for the purposes of this summary.

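### Extra-renal flares after early IP discontinuation are liable to be under-counted, because the minimum assessment set omits SLEDAI-2K and the flare instrument

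*Protocol*

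**What the plan says.** **Default after IP is stopped.** Protocol 3.9.9 states: "Subjects who are discontinued from the IP should be followed up to continue to undergo all study-related visits/procedures for the full treatment period". Footnote b to Table 2 agrees: "Subjects with early discontinuation of IP should continue to attend visits according to the Study Plan". Table 4 carries the same footnote. The flare instrument is marked at every visit from Week 0 in Table 2 and at every visit in Table 4.

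**Floor beneath the default.** Protocol 4.2.2 says "Subjects who discontinue IP will be asked to return for all regular clinic visits", and then "All study assessments will be performed if possible; however, at a minimum, the following". The list names lupus serology, PGA, 24-hour urine and spot UPCR, safety laboratory tests with urinalysis, vital signs, physical examination and weight, adverse events, the TB questionnaire and concomitant medications. SLEDAI-2K and the flare instrument are not on it. Section 3.9.9 directs a subject who "wishes to continue with only selected study assessments; prioritised assessments are listed in Section 4.2.2".

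**Telephone option.** Under 4.2.2, a subject who declines all clinic visits may be called monthly for 12 weeks after the last dose. The calls cover adverse events, lupus symptoms and lupus medications, and steroid bursts are captured. They do not include either instrument.

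**Reporting.** SAP 4.2.6.4 states: "The flare rate per of subject years for extra-renal flares will be presented overall, and by timing". The split is on treatment versus off treatment, and off treatment begins 28 days after the last dose.

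**The concern.** Extra-renal flare by this instrument is a named outcome of the safety objective (Protocol 2.3) and a key safety assessment (Protocol 5.2). The minimum set is where a site looks when a subject will not do everything, and it drops the instrument only in subjects who have stopped IP.

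Other data do not fill the gap. Protocol 6.5.7 keeps disease worsening out of adverse-event reporting unless it is serious, and sends it to SLEDAI-2K, PGA and PtGA. Of these, only PGA is in the minimum set. SAP 3.6.4 also needs the change in non-renal SLEDAI-2K and new or worse manifestations, and no visible rule derives a flare from PGA alone. SAP 4.1.4 says missing safety data will generally not be imputed.

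At stake is whether a reader can tell fewer flares from fewer forms when comparing off-treatment with on-treatment rates, or the overall rates between arms.

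**Working it through.** The plan states no flare rate or completion rate, so there is no figure of its own to reproduce. The check has four steps.

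**1. Where the schedule leaves no gap.** A subject who completes year 1 has the last dose at Week 48. Adding 28 days, off-treatment time starts at Week 52. The 8 weeks to Week 60 carry flare assessments at Weeks 56 and 60 (Table 3), the same four-weekly spacing as on treatment. Extension completers have the same pattern at Weeks 108 and 112 (Table 5). Any gap is confined to early discontinuers.

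**2. Where a gap can open.**
- Telephone-only follow-up lasts 12 weeks after the last dose. Taking off the first 4 weeks leaves 8 weeks of off-treatment time with no instrument.
- The look-back is 30 days (Protocol 5.2.8; SAP 3.6.4). If one four-weekly assessment is skipped, the next comes 56 days after the last one, so 56 − 30 = 26 days fall outside the look-back.

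**3. Illustrative size, all off-treatment time in the denominator.** Every input here is an assumption. Early discontinuers, a share p of subjects, stop IP at about Week 24 and contribute Weeks 28 to 52, which is 24 weeks. All others contribute 8 fully assessed weeks. The true flare rate is the same in both groups, a fraction f of the early discontinuers' assessments is done, and a missed assessment counts no flare.

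Reported/true rate = [24pf + 8(1 − p)] / [24p + 8(1 − p)]

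| p | f = 0 | f = 0.5 | f = 1 |
|---|---|---|---|
| 10% | 7.2/9.6 = 0.75 | 8.4/9.6 = 0.88 | 1.00 |
| 20% | 6.4/11.2 = 0.57 | 8.8/11.2 = 0.79 | 1.00 |
| 30% | 5.6/12.8 = 0.44 | 9.2/12.8 = 0.72 | 1.00 |
| 40% | 4.8/14.4 = 0.33 | 9.6/14.4 = 0.67 | 1.00 |

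Among early discontinuers alone the ratio is simply f. The pooled figures are closer to 1 because completers' follow-up is fully scheduled.

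**4. Would counting only assessed time cure it?** Let flare risk per visit be λ, and let the form be completed with probability g if there is a flare and f if there is not (all assumed).

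Assessed-time rate / true rate = g / [λg + (1 − λ)f]

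- λ = 0.05, f = 0.5, g = 0.9: 0.9/(0.045 + 0.475) = 1.73
- λ = 0.10, f = 0.5, g = 0.9: 0.9/(0.09 + 0.45) = 1.67
- λ = 0.05, f = 0.9, g = 0.5: 0.5/(0.025 + 0.855) = 0.57
- f = g: 1.00

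In the first two cases the all-time rate would be 0.9 of the truth, so the assessed-time rate is the more distorted of the two. An assessed-time denominator is unbiased only if completion is unrelated to flare.

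**The case against.** The strongest reply is that the list is a floor and not the schedule. Sections 3.9.9 and 4.2.2, footnote b of Tables 2 and 4, and SAP 1.2.5 all keep early discontinuers on the full schedule. Even a subject unwilling to continue to Week 52 or 104 is asked to complete that visit and the follow-up visits, which carry both instruments. This stands. A reader might infer that the off-treatment rate is low by construction. The documents do not support that, because nothing in the plan forces an assessment to be missed.

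A reader might also infer that off-treatment time comes mostly from subjects stopped for worsening disease. That is not shown either. The category includes all IP completers in safety follow-up, and early stops also include adverse events and subject decision (Protocol 3.9.4).

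Third, the denominator cannot be called wrong. The SAP's version 5.0 change log refers to a flare exposure time, and much flare-related text is redacted. The rule may exist there, or may cover renal flares only. What can be said is that the visible text of 4.2.6.4 gives no rule for missed assessments.

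Finally, the reduced list helps retention, and the instrument needs a certified assessor. The second point carries little weight: PGA is already on the list and needs certification too (Protocol 9.1.1).

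**Conclusion.** The point holds as a risk of under-ascertainment among early discontinuers. It does not hold as a demonstrated bias. Two facts are firm: both instruments are outside the minimum set and the telephone route, and the SAP reports flare rates on and off treatment with no visible rule for missed assessments.

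The size is unknown. The 0.88 to 0.67 range at half completion rests on an assumed 10% to 40% of early discontinuers, a stop at about Week 24, equal true flare rates, and all off-treatment time being counted. With complete forms the effect is nil.

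A reader might go on to infer that stopping the drug will look safer than it is, or that one arm's overall rate is flattered. Either would need completion rates and off-IP time by arm, which the documents do not give. The output is descriptive and outside the testing hierarchy in SAP 4.1.2, so the primary and secondary conclusions are not affected. The change is worth making because it is cheap and makes ascertainment more even on and off IP.

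**What to change.** 1. **Protocol 4.2.2:** add SLEDAI-2K and the SLEDAI-2K based Flare Assessment Instrument to the minimum assessments. Their main inputs (physical examination, serology, urinalysis and PGA) are already required there, as is a certified assessor for PGA.
2. **SAP 4.2.6.4:** beside the flare rates, report the number of completed flare assessments per subject-year, on and off treatment, by arm. This also exposes telephone-only time, which the first change cannot reach.
3. **SAP 4.2.6.4:** if a rate based only on assessed time is shown, present it as a supplement to the all-time rate, because it is biased upward if forms are completed more often when a flare occurs.

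The cost is one line in the protocol list, a short addition to the SAP, and one more form with slightly more burden at off-IP visits. No additional staff are needed.

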3.9.5 Subject decision to discontinue investigational product

If the subject decides to discontinue IP for any reason including but not limited to those outlined in Section 3.9 above, the subject will not receive any further IP. Subjects who discontinue IP during the 52 week double-blind treatment period will be followed until Week 52 (or for a minimum of 12 weeks after last dose of IP for subjects for whom IP was discontinued within 12 weeks prior to Week 52). If discontinuation occurs during the second year extension period, subjects will be followed until Week 104 (or for a minimum of 12 weeks after last dose of IP for subjects for whom IP was discontinued within 12 weeks prior to Week 104). The subject may continue to receive Sponsor-provided MMF until the end of the subject's participation in the study.

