5.2.10 Safety laboratory tests

The following are the laboratory-based safety assessments:

- Screening laboratory tests
- Haematology
- Serum chemistry
- Lipid profile
- Urine analysis
- Pregnancy tests

A Laboratory Manual will be provided to the sites that specifies the procedures for collection, processing, storage, and shipment of samples, as well as laboratory contact information, specific to this clinical research study.

All clinical laboratory tests will be performed in a central clinical laboratory at the times indicated in the Study Plan ([Table 2](#), [Table 3](#), [Table 4](#), and [Table 5](#)).

A serum pregnancy test (or serum FSH in post-menopausal females with menses absent for ≥ 1 year) will be performed at screening at the central laboratory. If the result of the serum β hCG test is borderline or thought to be false positive the test can be repeated during the screening. The subject can continue if the repeat test is negative. At every visit after screening, urine pregnancy tests will be performed at the site using a dipstick. During the treatment period, urine pregnancy tests should be performed at each visit before administering the IP and Sponsor-provided MMF. Abnormal safety laboratory results should be repeated as clinically indicated, as soon as possible (preferably within 24 to 48 hours).

Additional safety samples may be collected if clinically indicated at the discretion of the Investigator.

Every attempt should be made to redraw any missing safety or efficacy laboratory tests, even if the subject has received the IP.

The Investigator should make an assessment of the available results with regard to clinically relevant abnormalities. The laboratory results should be signed and dated and retained at the centre as source data for laboratory variables. For information on how AEs based on laboratory tests should be recorded and reported, see Section 6.5.

In case a subject shows an AST or ALT $\geq 3 \times \text{ULN}$ or total bilirubin $\geq 2 \times \text{ULN}$ please refer to [Appendix D](#) 'Actions required in cases of combined increase of Aminotransferase and Total Bilirubin – Hy's Law', for further instructions.

The laboratory variables that will be measured are summarised in Table 6.

Table 6 Clinical laboratory tests

Screening only test

Haemoglobin A1c (HbA1c; diabetic subjects only)

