6.9.1 Maternal exposure

If a subject becomes pregnant during the course of the study, IP and Sponsor-provided MMF should be discontinued immediately.

Pregnancy itself is not regarded as an AE unless there is a suspicion that the IP under study may have interfered with the effectiveness of a contraceptive medication. Congenital abnormalities/birth defects and spontaneous miscarriages should be reported and handled as SAEs. Elective abortions without complications should not be handled as AEs. The outcome of all pregnancies (spontaneous miscarriage, elective termination, ectopic pregnancy, normal birth or congenital abnormality) should be followed up and documented even if the subject was discontinued from the study.

If any pregnancy occurs in the course of the study, then the Investigator or other site personnel informs the appropriate AstraZeneca representatives or designee within 1 day, ie, immediately but **no later than 24 hours** of when he or she becomes aware of it.

The designated AstraZeneca representative works with the Principal Investigator to ensure that all relevant information is provided to the AstraZeneca Patient Safety data entry site within 1 or 5 calendar days for SAEs (see Section 6.6) and within 30 days for all other pregnancies.

The same timelines apply when outcome information is available.

Any subject who becomes pregnant during the course of the study will be followed up until the outcome of pregnancy is known so that the pregnancy outcome can be determined and reported to AstraZeneca or designee and the regulatory authorities.

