Subject with premature discontinuation of IP will continue to receive Sponsor-provided MMF (unless subject is pregnant) at the investigator's discretion until subject's participation ends.

Initial adjustment of MMF dose to achieve or maintain the target dose (Randomisation through Week 8)

- Subjects who are receiving MMF at a dose of 2 gm/day at Week 0 (Day 1) will continue this dose
- Subjects who are not taking MMF at Week 0 (Day 1), or subjects who are taking less than 2 gm/day, the dose will be titrated up with the goal of achieving a dose of 2 gm/day (or the therapeutic target dose if local

treatment standards dictate a lower dose) by Week 2 (but not later than Week 8, if dose escalation is limited by intolerability).

Titration of MMF should follow accepted local practice guidelines, including appropriate laboratory monitoring for toxicity.

- Subjects, who at Week 0 (Day 1) are taking MMF doses >2 gm/day will have their dose reduced to 2 gm/day by Week 8 unless they meet criteria for suboptimal response (see below for suboptimal response)

MMF dose between Week 8 and 24

The dose of MMF will be kept stable from Week 8 through Week 24 unless dose escalation to a maximum of 3 gm/day is necessary for suboptimal response (defined below) or a dose reduction is necessary to manage toxicity or intolerability.

Criteria for suboptimal response:

A suboptimal response is defined by UPCR values shown below at two independent measurements taken at least 2 weeks apart:

- Spot UPCR >3 mg/mg and
- Spot UPCR <15% decrease compared to baseline spot UPCR

If a subject meets the criteria at or after Week 8, the dose may be escalated or kept above 2 gm/day. After initial confirmation of suboptimal response, MMF can be increased up to 3 gm/day until Week 16 without re-testing for the suboptimal response criteria. The dose of MMF must be kept stable from Week 16 unless suboptimal response criteria are met or dose reduction is necessary for intolerability or MMF-related AEs. A temporary decrease below the minimum dose, or withholding MMF for 14 days or less, for MMF-related side effects, such as gastrointestinal side effects, for cytopenias or infection is acceptable.

Mycophenolate mofetil dose between Week 24 and Week 52:

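### The minimum assessment set after IP is stopped omits the urine pregnancy test, although Sponsor-provided MMF may continue and Protocol Section 5.2.10 still requires the test

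*Protocol*

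**What the plan says.** **The default after IP is stopped.** Section 3.9.9 keeps subjects on the full schedule: "Subjects who are discontinued from the IP should be followed up to continue to undergo all study-related visits/procedures for the full treatment period". Footnote b of Tables 2 and 4 likewise keeps them on the Study Plan.

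**The reduced set.** For a subject who stops IP permanently and "wishes to continue with only selected study assessments; prioritised assessments are listed in Section 4.2.2", Section 3.9.9 points to Section 4.2.2, which reads: "All study assessments will be performed if possible; however, at a minimum, the following assessments should be completed". Its first list holds lupus serology, PGA, and the 24-hour and spot urine measurements. Its safety list holds "Serum chemistry, haematology, urinalysis", vital signs, physical examination and weight, adverse events, the TB questionnaire and concomitant medications. Neither list has a pregnancy test.

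**MMF after IP.** Section 7.7.3.1: "Subject with premature discontinuation of IP will continue to receive Sponsor-provided MMF (unless subject is pregnant"), at the investigator's discretion, up to the end of participation. Section 3.9.5: "The subject may continue to receive Sponsor-provided MMF until the end" of participation.

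**Pregnancy testing.** Section 5.2.10: "At every visit after screening, urine pregnancy tests will be performed at the site using a dipstick". It adds that in the treatment period the test comes before both IP and Sponsor-provided MMF.

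**Action on pregnancy.** Section 6.9.1: "If a subject becomes pregnant during the course of the study, IP and Sponsor-provided MMF should be discontinued immediately".

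**The concern.** Continued MMF after IP is stopped depends on the subject not being pregnant, and Section 6.9.1 requires MMF to stop at once if she becomes so. Both provisions depend on the pregnancy being detected. The protocol's routine means of detection is the urine test in Section 5.2.10, but the list written for subjects who will not do everything leaves that test out.

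A site can therefore meet the stated floor of Section 4.2.2 in full and go on dispensing MMF without the test. Section 6.11.3 names foetal loss and congenital malformation as risks of MMF, and Section 6.9 requires pregnancies to be reported. At stake are undetected foetal exposure to a drug that the sponsor supplies and late or missing pregnancy reports. The efficacy analyses, alpha and power are untouched.

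**Working it through.** No statistical figure is involved. The check is a comparison of sections, plus a count of visits.

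**Step 1. Is the test covered under another name?** Urinalysis is in the minimum list, but the pregnancy test has its own row in Tables 2 and 4 and its own heading in Table 6. Urinalysis therefore does not include it.

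**Step 2. Does the requirement lapse when IP stops?** No.
- The every-visit sentence in Section 5.2.10 is not limited to subjects on IP, and the sentence after it ties the test to MMF as well as to IP.
- Table 3 marks the urine pregnancy test at Weeks 56 and 60, after IP has ended, and marks MMF dispensing at Week 56. Table 5 does the same for Weeks 108 and 112, with MMF dispensed at Week 108.
- The plan thus expects testing to go on off IP.

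**Step 3. Does either section settle the matter?** Section 4.2.2 does not refer to 5.2.10, and 5.2.10 does not refer to 4.2.2. Neither says which governs a subject on the reduced set.

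**Step 4. Who is affected?** A subject must meet all of these conditions: female of childbearing potential, IP stopped early, followed on the minimum set, and still receiving Sponsor-provided MMF.

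**Step 5. How long can it last?** Visits are four-weekly, and Tables 2 and 4 mark both MMF and the pregnancy test at each visit from Week 0 to Week 104. Remaining visits = (last scheduled week − week IP is stopped) / 4.

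| IP stopped at | Followed to | Remaining visits |
|---|---|---|
| Week 12 | Week 52 | (52 − 12)/4 = 10 |
| Week 24 | Week 52 | (52 − 24)/4 = 7 |
| After the Week 0 dose | Week 52 | (52 − 0)/4 = 13 |
| After the Week 52 dose | Week 104 | (104 − 52)/4 = 13 |

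Weeks 12 and 24 are the protocol's own checkpoints for stopping IP (Section 3.9.2). The last two rows are the longest cases. These are visits at which the two sections differ for a subject on the minimum set, not visits at which a test is known to be missed.

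**The case against.** The strongest reply is that the texts can be followed together. A floor does not cancel a requirement stated elsewhere. Section 4.2.2 asks first for all assessments where possible, 3.9.9 and the table footnotes keep the full schedule as the default, and 5.2.10 carries no exception. A site that dispenses MMF untested has departed from 5.2.10. Section 3.9.9 also introduces the prioritised list in a paragraph about preserving study data, so the list need not be read as the conditions for dispensing MMF. Other safeguards continue: contraception until 6 weeks after the last MMF dose (inclusion criterion 11), the investigator's discretion over MMF, and adverse-event review at visits.

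Much of this stands, and it rules out three stronger readings that a reader might infer:
- **That the protocol tells sites to skip the test.** It does not. Section 5.2.10 is not waived, and the reduced set is a fallback.
- **That a site on the minimum set cannot know whether a subject is pregnant.** This goes too far. Such a site has still to follow 5.2.10, and pregnancy may come to light in other ways.
- **That a particular number of women or visits is exposed.** The documents give no rate of early discontinuation, of choosing the reduced set, or of continuing MMF. Some women will also have left MMF: one IP-stopping criterion in Section 3.9.1 is MMF discontinuation with another immunosuppressant started.

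The reply does not remove the inconsistency. A minimum list exists because some subjects will decline procedures, and a site using it is not told that an omitted item remains mandatory for anyone still on MMF.

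**Conclusion.** The point holds as an internal inconsistency of limited scope. The Section 4.2.2 minimum set omits a test that Section 5.2.10 requires at every visit and links to MMF, while 3.9.5 and 7.7.3.1 allow the same subjects to stay on MMF and 6.9.1 relies on pregnancy being recognised.

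For a woman of childbearing potential on the reduced set and still on MMF, it can span 10 visits after a Week 12 stop, 7 after a Week 24 stop, and at most 13 within either year. This assumes that she attends the four-weekly schedule and that MMF continues throughout. The number of such women is unknown from the documents and is not estimated here.

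It is worth correcting because of the safety interest and the small effort. It has no bearing on sample size, error control or the efficacy results.

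**What to change.** Reconcile Section 4.2.2 with Sections 5.2.10, 6.9.1 and 7.7.3.1, so that the minimum list is consistent with the pregnancy testing that 5.2.10 already requires for subjects still receiving Sponsor-provided MMF. Section 3.9.9, which points to the list, then needs no change of its own. This aligns existing text and proposes no new clinical rule.

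The cost is about one line in Section 4.2.2. At the visits concerned, the work is a dipstick that 5.2.10 already calls for, and the minimum set already includes urine collection.
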